We will add apremilast to their treatment regimen according to the approved dosage for psoriasis and psoriatic arthritis: 10 mg orally one time on day 1, 10 mg orally twice daily on day 2, 10 mg orally in

AM and 20 mg orally in PM on day 3, 20 mg orally twice daily on day 4, 20 mg orally in AM and 30 mg orally in PM on day 5, then 30 mg orally twice daily thereafter.

7. Brief Study Synopsis: With limited treatment options available for dermatomyositis, we hypothesize that apremilast, a phosphodiesterase-4 (PDE-4) inhibitor, is a safe and efficacious add-on treatment in patients with recalcitrant cutaneous dermatomyositis.

The study will investigate the efficacy, safety and toxicity of apremilast given at 30 mg twice daily to patients with recalcitrant cutaneous dermatomyositis. Clinical response will be assessed at 1 and 3 months. Patients will also be evaluated for durability of their response for up to 6 months.

Treatment will be monitored with frequent clinical visits (0, 1, 3 and 6 months) and blood tests (CBC, CMP, CK, aldolase). Treatment will be discontinued at disease progression or unacceptable adverse events. Disease progression is defined as a 4 points increase in CDASI score, worsening of muscle disease by MMT-8 score and 5 points increase in DLQI.

5 mm skin biopsies from lesional skin will be performed before treatment with apremilast and after 3 months of treatment for gene expression profiling and confirmatory immunohistochemical stains.

8. Inclusion Criteria:

- Must understand the risks and the benefits/purpose of the study and provide signed and dated informed consent.
- Must be 18 years at time of signing the informed consent form.
- Willing to participate in all required evaluations and procedures in the study including the ability to swallow pills without difficulty.
- Patients must have a diagnosis of DM based upon the characteristic cutaneous findings proposed by Sontheimer^[6] and/or a skin biopsy consistent with DM.
- Patients must be candidate for systemic therapy for their DM skin disease defined by inadequate response to aggressive sun protection along with the use of potent topical corticosteroids and/or immunomodulators.
- Patients with a diagnosis of dermatomyositis on steroid-sparing agent and/or systemic steroids (maximum dose of prednisone 1mg/Kg) and still having cutaneous disease activity of at least 5 on the CDASI scale.

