- Prior history of suicide attempt at any time in the patient's lifetime prior to screening or randomization, or major psychiatric illness requiring hospitalization within the last 3 years.
- Active substance abuse or a history of substance abuse within 6 months prior to screening.
- Use of any investigational drug within 4 weeks prior to randomization, or 5 pharmacokinetic/pharmacodynamic half-lives, if known (whichever is longer).
- Prior treatment with apremilast.
- Any severe systemic illness requiring IV antibiotics within the two weeks prior to initiation of the study drug.
- Malignancy or history of malignancy within the past four years, except for:
 - treated [ie, cured] basal cell or squamous cell in situ skin carcinomas;
 - treated [ie, cured] cervical intraepithelial neoplasia (CIN) or carcinoma in situ of cervix with no evidence of recurrence within the previous 4 years.

10. Sampling and correlative analysis

Although, the proposed mechanism of action of apremilast is through PDE-4 inhibition resulting in c-AMP upregulation, the exact biological process that leads to dermatological response in dermatomyositis remains ill-defined. We propose to perform gene expression profiling (GEP) using RNA sequencing on skin biopsies collected before and after treatment with apremilast. In addition, we plan to confirm our GEP findings at the protein level using immunohistochemical (IHC) stains.

A. Tissue sampling and preparation

a. Tissue collection

5 mm punch biopsy from dermatomyositis skin lesions will be performed at baseline and another 5 mm punch biopsy will be performed at the 3-month time point. Each biopsy will be vertically split in two pieces and snap frozen on dry ice then it will be stored at -80C for further analysis with RNA sequencing and IHC stains.

b. RNA extraction

At the end of all timeline collections, each skin biopsy will be mechanically broken down followed by mRNA extraction using the RNeasy extraction Kit from QIAGEN. mRNA will then be stored at -80°C for subsequent RNA sequencing as detailed below.

B. Correlative Analysis

Determining the mechanism of action of apremilast in dermatomyositis.

a. Gene expression profiling

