RNA extracted from skin biopsies collected before and after *in vivo* treatment with apremilast (as detailed above) will be subjected to RNA sequencing. Illumina strand-specific TruSeq libraries will be prepared from the polyA selected RNA and subjected to 1x100 base sequencing on an Illumina HiSeq2500 machine. The number of samples proposed here (10 samples before treatment and 10 samples after treatment) is expected to yield sufficient statistical power for this approach; smaller numbers have been used in similar approaches to investigate drugs' mechanism of action (usually three samples).^[7-9]

RNA-seq analysis will be performed in conjunction with the Tulane Cancer Crusaders Next Generation Sequence Analysis Core (Tulane Cancer Center - <https://tulane.edu/som/cancer/research/core-facilities/cancer-crusaders/>). Gene and isoform expression will be determined using RSEM^[10] and differential expression will be analyzed using EB-seq.^[11] Genes that are identified as differentially expressed between the two groups with a False Discovery Rate (FDR) of < 0.05 will be subjected to analysis by *Ingenuity* (IPA, Redwood City, CA). This analysis will group the identified genes into specific pathways, cell types, or disease process. A similar approach will be conducted using *Gene Set Enrichment Analysis (GSEA)*. These experiments and GEP analysis will be performed in conjunction with our collaborator's ([name]) lab, given his extensive experience in this field.^[12, 13]

b. Protein analysis

Information identified by Ingenuity or GSEA (signaling pathways, regulatory molecules, etc...) will be verified using IHC staining on select samples.

IV. OBJECTIVES AND ENDPOINTS

1.Primary Objective Description

To determine the overall response rate (ORR) of apremilast in cutaneous disease of patients with recalcitrant dermatomyositis at 3 months.

The ORR will be measured using the Cutaneous Dermatomyositis Activity and Severity Index (CDASI) at months 0, 1, and 3.

CDASI is a validated tool to measure skin disease activity in dermatomyositis.^[14] ORR includes partial and complete responses. Complete response is defined by a CDASI score of zero. Partial response is defined by a decrease of CDASI score of at least 4 points. Calculation is performed as the CDASI score at 1, and 3 month(s) minus the score at baseline.

All investigators (PI and Sub-Is) will be trained on how to screen the patients per the CDASI score tool.

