Skin biopsies from lesional skin will be performed before treatment with apremilast and after 3 months of treatment for gene expression profiling and IHC stain. IHC will be performed on the protein product of the genes showing the largest fold change from the RNA-sequencing.

All investigators (PI and Sub-Is) will be trained on how to screen the patients per the MMT-8 score tool.

V. STUDY ENROLLMENT AND TIMELINES

1. # of Patients Expected to Enroll: 10

2. Date of planned FSI: 04/02/2018

3. Date of planned LSI: 11/01/2018

4. Date of planned LSO: 05/01/2019

5. Patient treatment duration (# months): 6 months

6. Is an interim Analysis Planned? Yes

7. Date on planned Interim Analysis: 03/01/2019

8. Date of planned final report: 06/03/2019

9. Are patients reported outcomes measured: Yes

VI. STATISTICAL PLAN:

Results of the study will be analyzed using descriptive statistics:

- Proportion of patients with complete ORR at 1,3 months
- Proportion of patients with partial ORR at 1,3 months
- Proportion of patients with complete durability response at 6 months for the 3 months responders
- Proportion of patients with partial durability response at 6 months for the 3 months responders
- Proportion of patients with complete response at 6 months
- Proportion of patients with partial response at 6 months
- Mean change from baseline in muscle enzymes (CK and aldolase in patients with muscle disease)
- MMT-8 change will be calculated as mean change from baseline at 1,3 and 6 months
- DLQI change will be calculated by identifying the proportion of patients with minimal clinically important difference of at least 5 points.

Missing data will be handled using the last observation carried forward approach (LOCF).

GEP will be analyzed using inferential statistics with a False Discovery Rate (FDR) of < 0.05 .

VII. INFORMED CONSENT:

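### The gene-expression comparison is written as two groups although the before and after biopsies are matched by patient; a patient-block analysis would find more changed genes if within-patient correlation exceeds about 0.2

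*Combined protocol and SAP*

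**What the plan says.** Section V gives "of Patients Expected to Enroll: 10" as the planned size. The Brief Study Synopsis (III.7) states that "5 mm skin biopsies from lesional skin will be performed before treatment with apremilast and after 3 months of treatment", and Tissue collection (III.10.A.a) repeats the schedule: one punch biopsy is "performed at baseline and another 5 mm punch biopsy will be performed at the 3-month time point". Gene expression profiling (III.10.B.a) counts "10 samples before treatment and 10 samples after treatment".

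For the analysis, III.10.B.a says that "differential expression will be analyzed using EB-seq", for genes and isoforms. It passes to Ingenuity "Genes that are identified as differentially expressed between the two groups with a False Discovery Rate (FDR) of < 0.05", with a similar approach by GSEA. Section VI adds only that inferential statistics at the same FDR will be used. The number of samples "is expected to yield sufficient statistical power for this approach"; the reason given is that similar work has used fewer, usually three.

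Immunohistochemistry (IHC) targets are reached by two routes. Under Protein analysis (III.10.B.b), findings from Ingenuity or GSEA are verified by IHC. Under Exploratory Objectives (IV.3), "IHC will be performed on the protein product of the genes showing the largest fold change from the RNA-sequencing".

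**The concern.** Ten patients with one biopsy at each of two times make ten pairs. An analyst who follows III.10.B.a as written would compare 10 samples with 10 others and leave differences between patients in the error term. If a patient's two biopsies resemble each other, that error term is too large for a before/after contrast, and truly changed genes can miss the FDR cut-off.

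What is at stake is the mechanism question. This is the only analysis for which Section VI plans inference, and the FDR list is the input to Ingenuity and so to the IHC step in III.10.B.b. The IV.3 route is less exposed: with all pairs complete, the mean log fold change is the same whether or not pairing is used. Response rate, durability, safety and DLQI are not involved.

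The power statement is a separate gap. It cites precedent and gives no detectable change, SD or correlation.

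**Working it through.** **No stated figure to reproduce.** The power claim is qualitative, so what follows is an illustration.

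**Inputs from the protocol:** n = 10 pairs; FDR < 0.05.

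**Assumed inputs:** 20,000 genes, 5% of them (1,000) changed by 1.5 SD, equal SD at both times, within-patient correlation rho from 0 to 0.5, gene variances spread with prior df 4, moderated t-tests, Benjamini-Hochberg at 5%. EB-seq was not run.

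**Step 1: why ignoring the pairs is conservative.** The true variance of the mean change is 2·SD²·(1 − rho)/n, but the two-group test uses 2·SD²/n. In the normal approximation its true size is 2·[1 − Φ(z/√(1 − rho))]. At nominal 0.05:
- rho 0.3: z/√0.7 = 1.96/0.837 = 2.34, size 0.019.
- rho 0.5: z/√0.5 = 1.96/0.707 = 2.77, size 0.006.

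**Step 2: what the block costs.** Residual df fall from 18 to 9; with prior df 4 that is 22 against 13. At rho 0 the two-group test finds 353 of the 1,000 changed genes with realised FDR 0.044. Its list has 353/0.956 = 369 genes, so the Benjamini-Hochberg cut-off is about 0.05 × 369/20,000 = 0.0009. At p = 0.001 the two-sided critical values are 3.79 (22 df) and 4.22 (13 df). The two tests need the same observed change when 3.79 = 4.22·√(1 − rho), that is rho = 1 − (3.79/4.22)² = 0.19. Hence the break-even at about 0.2.

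**Step 3: simulation.** Share of truly changed genes found:

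| rho | two-group | patient block | two-group realised FDR |
|---|---|---|---|
| 0 | 35% | 20% | 4.4% |
| 0.1 | 34% | 28% | 2.8% |
| 0.2 | 33% | 37% | 1.6% |
| 0.3 | 32% | 50% | 0.8% |
| 0.5 | 31% | 79% | 0.1% |

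The block's realised FDR was 4.1% to 4.8%. On 1,000 changed genes, rho 0.3 means about 320 against 505 found.

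**Step 4: sensitivity to the assumptions** (two-group against block).
- rho 0.3, 1% of genes changed: 6% against 16%. With 10% changed: 50% against 67%.
- Negative binomial counts on log-CPM: rho 0, 28% against 17%; 0.2, 25% against 30%; 0.3, 25% against 41%; 0.5, 21% against 64%.
- 8 complete pairs plus 2 baseline-only patients: rho 0, 24% against 4%; 0.2, 22% against 14%; 0.3, 19% against 23%; 0.5, 18% against 53%. The break-even moves to between 0.2 and 0.3.

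**Step 5: an alternative paired model.** One within-patient correlation estimated across all genes finds more: 35%, 55%, 67% and 89% at rho 0, 0.2, 0.3 and 0.5. If rho differs between genes (SD 0.2), however, its realised FDR is 5.9% to 6.9% for mean rho 0 to 0.5 and 9.2% at 0.7. With SD 0.3 or only 1% of genes changed it is mostly 8% to 9%, and up to about 15% with both together. The block stays near 5%.

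**The case against.** The strongest reply is that this is an exploratory analysis in a 10-patient study and that nothing in the text forbids pairing. That stands: the protocol is silent on a patient term and does not rule one out.

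Second, the size of the loss rests wholly on assumptions. The protocol gives no correlation, SD, effect size or share of changed genes. It does not say that the month-3 biopsy comes from the same lesion or site, so a low correlation is possible, and then the block would be the weaker test. Whether EB-seq behaves like the t-test proxy has not been shown. All of this stands and limits the point to a conditional one.

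Three stronger readings are tempting, and none is supported.
- That ignoring the pairing produces false positives: with one common positive correlation the two-group test is conservative. It becomes liberal if the correlation is negative (size 0.083 at rho −0.3, nominal 0.05), and slightly so if the correlation varies between genes around zero (realised FDR 5.8%).
- That any positive correlation costs power: against the patient block this holds only above about 0.2.
- That the more powerful shared-correlation model should be the main analysis: it can exceed the FDR limit that the plan itself sets.

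**Conclusion.** The point holds in a limited form. The planned comparison is worded for two groups, the samples are matched by design, and no patient term is stated in the text supplied. In the illustration, following the text costs discoveries when within-patient correlation is moderate: 18 percentage points at rho 0.3 (32% against 50%) and 48 at rho 0.5 (31% against 79%). At rho 0 the two-group test is ahead by 15 points. These figures rest on a 1.5 SD change in 5% of genes and on a t-test proxy; the actual loss is unknown.

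A reader might infer that the mechanism study is underpowered or the trial's conclusions unsafe. The documents show neither. They show an unspecified use of the pairing and a power claim with no calculation behind it. This is a cheap improvement that the sponsor could make, not a fault that must be repaired before the clinical results can be used.

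**What to change.** In III.10.B.a:
- State that baseline and month-3 samples are matched by patient.
- Replace the two-group EB-seq comparison, for genes and isoforms alike, with a variance-moderated model that has time and patient (as a blocking factor), fitted to complete pairs at FDR < 0.05.
- Name that list as the one sent to Ingenuity, and use the same paired contrast for GSEA, so that the IHC verification in III.10.B.b rests on it.
- Report a shared within-patient-correlation model, which also keeps baseline-only patients, as a sensitivity analysis. Note that its FDR can exceed 5% if the correlation differs between genes, and that keeping those patients assumes that a missing month-3 biopsy is unrelated to the expression change.
- Delete the power statement, or replace it with the detectable paired change under stated assumptions. With the inputs above, the patient block reaches 80% average power at changes of 2.16, 1.91, 1.80 and 1.53 SD for rho 0, 0.2, 0.3 and 0.5 with 10 pairs, and 2.52, 2.22, 2.10 and 1.78 SD with 8 complete pairs.

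The cost is a different software call and a few sentences; no new samples are needed. The downsides are lower power than the two-group test if within-patient correlation is near zero, and the loss from the main gene list of any patient without a month-3 biopsy.

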Photograph of skin rash will be taken at months 0,1 and 3 and compared to baseline.

2. Secondary Objective(s) Description

To determine the durability of responses for up to 6 months on apremilast for responders at 3 months. The durability of responses includes partial and complete response durability. The durability of response will be measured using the CDASI at 6 months minus CDASI at 3 months. Complete response durability is defined as zero or minus difference between CDASI score at 6 months and CDASI score at 3 months. Partial response is defined as >4 points difference between CDASI score at 6 months and CDASI score at 3 months.

We will assess the response of all patients at 6 months to identify possible delayed response. Complete response is defined by a CDASI score of zero at 6 months. Partial response is defined by a decrease of CDASI score of at least 4 points at 6 months compared to baseline. Calculation is performed as the CDASI score at 6 month(s) minus the score at baseline.

Photograph of patient's rash will be taken at 6 months and compared to 3 months and baseline.

To determine the safety and toxicity of apremilast when administered at 30 mg twice daily in patients with dermatomyositis. The safety assessment will include the assessment of adverse events, serious adverse events, laboratory testing and physical examination.

An additional secondary endpoint will be to determine if patients who experience remission of their disease can be maintained on apremilast as monotherapy.

To determine the patient quality of life using the Dermatology Life Quality Index (DLQI)^[15] at baseline, 1, 3 and 6 months.

Patient will be assessed 1 month after discontinuing apremilast (follow up visit) to assess change in response post discontinuation of apremilast. Patients will be examined and, CDASI, MMT-8 and DLQI will be performed. Photograph of patient's rash will be taken. CBC, CMP, CK, aldolase and urine pregnancy test will be performed.

3. Exploratory Objectives:

We will measure muscle enzymes (creatin kinase (CK) and aldolase) at 0, 1, 3, and 6 month(s) of apremilast in patients with muscle disease.

We will assess disease activity using the manual muscle testing-8 (MMT-8) in patients with muscle disease.^[16]

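### Complete durability allows no rise at all from the single month-3 CDASI score that selected the responder, so an estimated quarter to over a half of unchanged responders would fail it, and a rise of 1 to 4 points has no category

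*Combined protocol and SAP*

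**What the plan says.** All references are to the combined protocol and SAP.

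- **Who is assessed** (IV.2, Secondary Objective(s) Description): "To determine the durability of responses for up to 6 months on apremilast for responders at 3 months".
- **The measure** (IV.2): "The durability of response will be measured using the CDASI at 6 months minus CDASI at 3 months". There is one score at each visit, with no repeat or confirmatory score.
- **Upper category** (IV.2): "Complete response durability is defined as zero or minus difference between CDASI score at 6 months and CDASI score at 3 months".
- **Lower category** (IV.2): "Partial response is defined as >4 points difference between CDASI score at 6 months and CDASI score at 3 months". The direction of the difference is not given.
- **What is reported** (VI, Statistical Plan): "Proportion of patients with complete durability response at 6 months for the 3 months responders", plus a matching line for partial durability. Missing data are handled by LOCF.
- **What makes a month-3 responder** (IV.1, Primary Objective Description): "Partial response is defined by a decrease of CDASI score of at least 4 points", or "Complete response is defined by a CDASI score of zero".
- **The plan's other CDASI threshold** (item 7, Brief Study Synopsis): "Disease progression is defined as a 4 points increase in CDASI score, worsening of muscle disease by MMT-8 score and 5 points increase in DLQI".

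IV.2 also assesses response at month 6 against baseline in all patients, to pick up delayed response. VI lists those proportions.

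**The concern.** Durability should show whether a response seen at month 3 is still there at month 6. The rule asks something narrower: whether the score failed to rise by even one point. A patient 15 points below baseline at month 3 and 14 points below at month 6 fails complete durability, yet is plainly still a responder under the plan's own month-6 rule.

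That patient has no other category either. A difference of +1 to +4 is not zero or negative, and it is not more than 4 in either direction. The plan thus leaves unclassified the small rises that scoring variation alone would produce most often.

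The reference score adds to this. Responders are selected because their month-3 score was low, and part of that lowness may be chance. The next score then tends to be higher even when disease is stable.

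Durability is the first-listed secondary objective, and there is no control arm to show how often stable patients fail the rule. A reader of the report could take scoring variation for loss of effect.

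**Working it through.** **No figure to reproduce.** The plan states no expected durability rate and no CDASI measurement error. The visit-to-visit SD is therefore an assumption, shown over a range.

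**Inputs from the plan.** Entry CDASI at least 5. Responder at month 3: fall of at least 4 points from baseline, or score 0. Complete durability: d = CDASI(month 6) − CDASI(month 3) ≤ 0. Enrolment: 10.

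**Step 1: the zero cut alone.** With no true change and no selection, rises and falls are equally likely (away from the floor at zero), so

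P(fail) = P(d > 0) = (1 − P(d = 0)) / 2.

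For whole-number scores with normal variation, P(d = 0) is 0.486, 0.271, 0.140 and 0.094 at SD 0.5, 1, 2 and 3. At SD 1, (1 − 0.271)/2 = 0.36. At SD 2, (1 − 0.140)/2 = 0.43.

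**Step 2: add selection on the month-3 score.** Simulation, 400,000 patients per scenario. Assumptions: true baseline uniform on 5–20 or 10–40; mean true fall by month 3 of 30% or 50%, with a between-patient SD of 20 percentage points; true score identical at months 3 and 6; observed scores rounded and floored at zero. Ranges are over the four combinations of baseline and fall, among observed month-3 responders.

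| Assumed visit SD | Fail, no selection | Fail complete durability | Rise of 1–4 (no category) | Rise above 4 | No longer meet response rule against baseline |
|---|---|---|---|---|---|
| 0.5 | 26% | 26–30% | 26–30% | 0% | 1–8% |
| 1 | 36% | 37–44% | 37–44% | 0.1% | 2–15% |
| 2 | 43% | 45–54% | 39–46% | 6–9% | 4–23% |
| 3 | 45% | 48–58% | 33–37% | 16–21% | 6–26% |

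- Selection adds about 0–4 percentage points at SD 0.5, 1–8 at SD 1, 2–11 at SD 2 and 3–13 at SD 3. The zero cut accounts for the rest.
- Across all scenarios, 22–42% of unchanged responders fail complete durability while still meeting the response rule against baseline.

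**Step 3: sensitivity to the scenario.** A second set of assumptions (mean baseline 10, 18 or 25; mean true fall 4, 6 or 10 points) gives failure of 19–28%, 30–41%, 38–51% and 41–56% at the same four SDs. The level shifts down somewhat; the pattern is the same.

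**Step 4: LOCF.** A missing month-6 score takes the month-3 value, so d = 0 and the patient passes. If missingness is unrelated to the score, the failure rate is multiplied by (1 − proportion missing). A rate of 50% becomes 0.50 × 0.90 = 45% with 10% missing, and 0.50 × 0.80 = 40% with 20% missing.

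**Step 5: what this means in a study of 10.** Suppose 5 patients respond (an assumption). Each failure moves the proportion by 1/5 = 20 percentage points. The chance that all five unchanged responders pass is 0.74^5 = 22% at a failure rate of 26%, and 0.42^5 = 1% at 58%.

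**The case against.** The strongest reply has four parts.

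*A strict no-worsening top category is a legitimate choice, and the endpoint is descriptive, in the responders among 10 patients, with no test or decision attached.* This limits the consequence. But a strict top category needs a usable category beneath it, and the plan's second category does not take in rises of 1 to 4 points. If it covered rises up to 4, over 99% of stable responders would be in one category or the other at SD 1, 91–94% at SD 2 and 79–84% at SD 3. Much of the harm therefore comes from the gap together with the zero cut.

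*Month-6 response against baseline is already reported.* True, and it means the reader is not left with the durability figure alone. A reader might infer that the trial cannot say anything about maintained response; that goes too far. But the existing line covers all patients and is not listed for month-3 responders, so it does not replace the durability result.

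*No stated failure rate can be read off the documents.* This stands. A reader might infer that half of stable responders must fail. That needs a visit SD of roughly 2 points or more, which the plan neither gives nor rules out. LOCF also lowers the rate, although this is no merit of the rule: a missing score passes and an observed 1-point rise fails.

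*Regression to the mean is a minor contributor.* This stands for the scenarios examined. Using the selecting score as reference is a real weakness, but the smaller one.

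**Conclusion.** The concern holds, with a conditional size. From the text alone: complete durability has no tolerance, its reference is the single score that defined the responder, and rises of 1 to 4 points have no durability category. With no true change after month 3, roughly a quarter to over a half of responders would fail, depending on an assumed visit SD of 0.5 to 3 points and on the assumed baselines and falls. LOCF reduces this in proportion to missing month-6 scores.

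A reader might also infer that most failures observed in the trial would be scoring noise. The calculation does not show that: it sets true change to zero, so every failure in it is noise by construction. It shows only that a low proportion could arise without any loss of effect. The definition should be changed before the durability proportions are reported.

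**What to change.** In IV.2 and the two durability lines of VI:

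1. Define a durable response as a month-3 responder who at month 6 still meets the plan's own response rule against baseline: CDASI at least 4 points below baseline, or zero.
2. Report how many month-3 complete responders are still at zero, as a description and not as the durability criterion. Otherwise the zero tolerance would persist for them.
3. List month-6 minus month-3 CDASI for each responder, with median and range, and the number who rose by 4 points or more. This is a reporting count only and says nothing about treatment.

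**Cost.** One definition and the matching lines in VI. The scores are already collected and the rule already exists for month 6.

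**Downsides.** A responder with a large month-3 fall can worsen substantially and still count as durable. For example, scores of 30 at baseline, 5 at month 3 and 26 at month 6 are a 21-point rise, yet 30 − 26 = 4 still qualifies. Item 3 makes such cases visible. Some stable responders near the 4-point threshold will still be misclassified: about 1–26% under the same assumptions. The change also leaves LOCF as it is, so a month-3 responder without a month-6 score would still count as durable; the number of carried-forward scores should be stated beside the result.

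### The durability line labelled as complete response does not require a complete response: any month-3 responder whose CDASI does not rise by month 6 is counted

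*Combined protocol and SAP*

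**What the plan says.** Section IV.1 sets the response terms. "Complete response is defined by a CDASI score of zero", and "Partial response is defined by a decrease of CDASI score of at least 4 points". The responder group contains both kinds: "ORR includes partial and complete responses". Section IV.2 repeats the zero-score definition for month 6.

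The first secondary objective in Section IV.2 is "To determine the durability of responses for up to 6 months on apremilast for responders at 3 months". It goes on: "The durability of responses includes partial and complete response durability", and "The durability of response will be measured using the CDASI at 6 months minus CDASI at 3 months". The rule for the complete category is "Complete response durability is defined as zero or minus difference between CDASI score at 6 months and CDASI score at 3 months". The companion rule for the partial category is a month-6 versus month-3 difference of more than 4 points, with no direction given.

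Section VI lists the reported line as "Proportion of patients with complete durability response at 6 months for the 3 months responders". It also lists, separately, the proportions with complete response at months 1 and 3 and at month 6.

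**The concern.** The protocol gives complete response one meaning, a score of zero. The durability rule uses the same term but tests only whether the score rose between months 3 and 6. It looks neither at whether the month-3 response was complete nor at whether the month-6 score is zero. Because the line runs over all month-3 responders, patients with durable clearance and patients holding a fall as small as 4 points go into one count under the stronger name.

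The study plans 10 patients and, for its clinical outcomes, descriptive proportions only, so the label on each proportion largely is the result. A reader who takes the label at its defined meaning would credit the drug with lasting complete responses that the protocol's own definition does not recognise.

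**Working it through.** The plan states no figure on this point, so there is none to reproduce. The check applies the written rules to individual records.

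**Inputs**
- Month-3 responder (IV.1): CDASI(3) = 0, or baseline − CDASI(3) ≥ 4.
- Complete response (IV.1, IV.2): CDASI = 0.
- Durability rule for the complete category (IV.2): d = CDASI(6) − CDASI(3) ≤ 0.
- Denominator (VI): all month-3 responders.
- Minimum entry score (inclusion criteria): 5.

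**Records** (hypothetical, chosen to exercise the rule)

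| Baseline, month 3, month 6 | Fall at month 3 | Month-3 category | d | Counted by the rule? | Zero at months 3 and 6? |
|---|---|---|---|---|---|
| 40, 36, 36 | 40 − 36 = 4 | partial | 36 − 36 = 0 | yes | no |
| 20, 12, 11 | 20 − 12 = 8 | partial | 11 − 12 = −1 | yes | no |
| 5, 1, 1 | 5 − 1 = 4 | partial | 1 − 1 = 0 | yes | no |
| 20, 0, 0 | 20 − 0 = 20 | complete | 0 − 0 = 0 | yes | yes |

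All four are counted; only the last is a durable complete response. The third record shows that this can happen even at the lowest permitted entry score.

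**Where the rule works and where it does not.** If CDASI(3) = 0, the score cannot fall further, so d ≤ 0 holds only when CDASI(6) = 0, and the rule is correct. A negative d is possible only when CDASI(3) > 0. The negative part of the rule therefore has effect only for patients who were not complete responders at month 3.

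**No complete responders at all.** The line then equals the share of partial responders whose score does not rise. That share is above zero as soon as one of them is stable or improves.

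**Can the other planned lines recover the answer?** Let a be the number at zero at month 3 and b the number at zero at month 6, among n = 10 patients. The number at zero at both visits lies between max(0, a + b − 10) and min(a, b). If a = 0 or b = 0, it is 0, and the separate lines show it. Otherwise they generally leave it open: with a = b = 1 (assumed), the two may be the same patient or two different patients, so the answer is 1 or 0.

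None of this depends on missing data or measurement error; it holds with complete, exact scores.

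**The case against.** The strongest reply is that the word complete grades the durability, not the response. Section VI's word order allows this, and two features of the text support it: a negative difference is impossible for a patient already at zero, and the denominator is all month-3 responders. On that reading a stable partial responder is counted by design, and the fault is one of naming. This stands as a possible intention. It does not rescue the wording, because Section IV.2 uses the protocol's defined term, directly after separating partial from complete response durability. Two analysts could fairly take the result to mean different things.

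The second reply is that complete response is reported separately at months 3 and 6. A reader might infer from the durability rule that the report would hide a total absence of clearance. The documents do not support that: both of those lines would read zero. What is lost is the patient-level link between the two visits.

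A reader might also want a number for the overstatement. The plan gives no expected response rate, score distribution or measurement error. Any simulated percentage would reflect the assumptions put in: with unchanged disease and no measurement error, every month-3 responder would be counted, and assumed error alone would bring the figure down.

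**Conclusion.** The point holds on the text. The line named for complete response durability counts any month-3 responder without a rise in CDASI, so it can be above zero with no complete response at any visit. If the intention was a fully maintained response of either kind, the rule is usable but its name contradicts the protocol's own definition. On either reading, no planned line states how many month-3 complete responses were still complete at month 6.

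The consequence is limited. This is a secondary, descriptive outcome; nothing is tested on it, the primary response rate is unaffected, and the separate zero-score lines bound the possible misreading. The documents do not support a stronger claim that the plan sets out to present partial responses as complete, or that the overstatement has a known size. The conclusion rests on the definitions alone. The change is worth making before the data are analysed.

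**What to change.** In Sections IV.2 and VI, report durability by month-3 category:

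- (a) Among month-3 complete responders: the number and proportion with CDASI zero at month 6.
- (b) Among month-3 partial responders: the number and proportion still meeting the protocol's own month-6 response definition, that is, at least 4 points below baseline, or zero.

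Make the categories exclusive. With a baseline of at least 5, a patient at zero has also fallen by at least 4 points, so partial should mean a fall of at least 4 with a score above zero. Under these rules the record 20, 0, 0 counts in (a). The other three count in (b), with month-6 falls of 40 − 36 = 4, 20 − 11 = 9 and 5 − 1 = 4. Line (b) also gives partial responders a rule with a stated direction.

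If the month-6 minus month-3 measure is kept, name it *no increase in CDASI since month 3* and split it by month-3 complete or partial response.

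The cost is a few lines of text. The Schedule of Events already collects CDASI at baseline and at months 3 and 6. The downside is small denominators, a less favourable figure, and possibly no month-3 complete responders at all; in that case (a) should be reported as not estimable.
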